2.2 Secondary Hypotheses

Secondary hypotheses examine the relative effectiveness of BSFT over TAU in:

Hypothesis 2a: Engaging adolescents and family members in treatment

Hypothesis 2b: Decreasing adolescent externalizing problem behaviors

Hypothesis 2c: Decreasing adolescent sexually risky behaviors

Hypothesis 2d: Increasing adolescent prosocial activities (e.g., school, work)

Hypothesis 2e: Improving family functioning (e.g., parenting, parent-adolescent relations).

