7.7.5 HIV/Sex Risk Behaviors (Hypothesis 2c)

Hypothesis 2c: BSFT will be significantly more effective than TAU in decreasing adolescent sexually risky behaviors.

- Risk Behavior Survey. *HIV risk* will be assessed using this 9-item questionnaire (CTN Common Assessment Battery; NIDA, 1991). The Risk Behavior Survey (RBS), an abbreviated version of the Risk Behavior Assessment (RBA) developed for a NIDA Cooperative Agreement (NIDA, 1991), will be used to measure HIV and HCV risk behaviors. HIV risk behaviors in the areas of drug use and sex in the previous 30 days are measured. Reliability and validity assessments of the RBS support its adequacy as a research tool for populations of drug users (Needle et al., 1995; Weatherby et al., 1994).

Most CTPs that have expressed interest in our protocol have a standardized procedure for screening HIV risky behaviors at intake. In case Risk is determined (i.e., non barrier use) patients will be counseled to seek HIV testing.

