Missing Data and Attrition. Analyses will be conducted to identify patterns of attrition and to determine if there is differential attrition by treatment condition. Attrition between conditions will be captured with the use of contact logs, and termination forms. To minimize any impact of attrition on the test of hypotheses, intent-to-treat analyses will be conducted for all hypotheses. Note that individuals that are placed in more restrictive settings for brief periods of time may continue to be included in subsequent assessments. Data will be collected for these individuals at all scheduled timepoints (if possible). The primary outcome measure will be used to identify days that the adolescent was placed in a restrictive environment.

Missing items from multi-item scales will be imputed using the Expectations Maximization (EM) algorithm (Little & Rubin, 1987); however, missing outcome measures (e.g. caused by missing an assessment) will not be imputed. Rather, the hypotheses will be modeled in an intent-to-treat fashion with a maximum likelihood algorithm, which allows the inclusion of cases with missing data (this is possible with the assumption that data are missing

at random). Note that the protocol calls for continued assessment of cases that drop out of intervention in the hope of minimizing all forms of missing data.

Reliability. When appropriate, reliability of all measures and outcomes will be assessed using confirmatory factor analysis. To confirm internal consistency reliability, estimates of Cronbach's alpha for each of the outcome variables (e.g., drug use, externalizing problem behaviors, family functioning) will be determined with a confirmatory factor analysis (Fornell & Larcker, 1981). The indicators of the outcomes in this protocol are scales of established reliability and validity. For any indicator/scale with an alpha < .70 (in this sample), items with low item-total correlations will be trimmed from the scale and the scale re-assessed for reliability. In the confirmatory factor analyses of the outcome variables based on these indicator/scales, should the overall fit of these models prove inadequate (Comparative Fit Index < .95 or standardized root mean squared residual > .06 (Hu & Bentler, 1999; Kline, 1998), additional modifications of the measurement model will be made to achieve an adequate fit. Specifics of the measurement models are described below under "Outcomes and Hypotheses".

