10.3 Secondary Outcomes and Hypothesis

There are five categories of secondary outcomes: a) engaging adolescents and family members in treatment, b) decreasing externalizing problem behaviors, c) decreasing adolescent sexually risky behaviors, d) increasing adolescent prosocial activities (e.g., school, employment), and e) improving family functioning (e.g., parenting, parent-adolescent relations). Please note that these secondary outcomes are only measured at B1, T4, T8 and T12.

Hypothesis 2a: BSFT will be significantly more effective in engaging participants in treatment than will TAU.

Outcome Variable. Engagement is defined as attendance by adolescent and/or family members at a minimum of two therapy (treatment) sessions. For BSFT, these will be BSFT sessions, for TAU, these will be defined in a manner that is consistent with the services provided (e.g., individual, group or non-manualized family therapy, day treatment).

Analysis. Hypothesis 2 will be analyzed as in Hypothesis 1 using hierarchical linear models (HLM) (Bryk & Raudenbush, 1992). However, in this analysis a logistic link function will be used due to the 0-1 nature of the outcome. Note that because this outcome is not a time-related value, that trajectories are not involved, however all other levels of nesting described in the primary analysis are still in effect and therefore HLM is still the method of analysis. In planned post-hoc analysis

[name]

engagement of adolescents and family members (i.e., attendance in therapy sessions), specifically will be examined.

Hypothesis 2b. BSFT will be significantly more effective than TAU in decreasing externalizing problem behaviors.

Outcome Variable. For Hypothesis 2b, a composite of the following scales will be used: ‘Total Delinquency’ from the National Youth Survey; ‘Oppositional Defiant Disorder’ and ‘Conduct Problems’ from the Diagnostic Interview Schedule for Children-Predictive Scales, and the ‘Externalizing Scale’ from the Youth Self-Report. A confirmatory factor analysis will be conducted to determine that these scales measure a single construct. Reliability of this construct when loadings are constrained to be 1 will be calculated and if sufficient, equally weighted composite scores will be constructed. Otherwise, factor scores will be created using the estimated loadings and the resulting composite will be used to examine hypothesis 2b.

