Analysis. The analyses for Hypothesis 2b is identical to the hierarchical linear models (HLM) (Bryk & Raudenbush, 1992) used to test Hypothesis 1. It is anticipated that no link function will be necessary.

Hypothesis 2c: BSFT will be significantly more effective than TAU in decreasing sexually risky behaviors

Outcome variable. For Hypothesis 2c, the total score of the ‘HIV/Sex Risk Behaviors’ measure will be used as the outcome.

Analysis. The analyses for Hypothesis 2c is identical to the hierarchical linear models (HLM) (Bryk & Raudenbush, 1992) used to test Hypothesis 1. It is anticipated that no link function will be necessary. The composite measure will be constructed using the methodology described in hypothesis 2b applied to the items of the Risk Behavior Survey from the Common Assessments Battery.

Hypothesis 2d. BSFT will be significantly more effective than TAU in increasing prosocial activities.

Outcome Variable. A composite measure will be verified using confirmatory factor analysis. Scales to be included in the composite and confirmatory analysis are the ‘Conventional Activities of Friends’ scale of the Pittsburgh Youth Survey, and the (negatively weighted) ‘Peer Delinquency’ scale from the Pittsburgh Youth Survey.

Analysis. Hypothesis 2d will be analyzed as in Primary Hypothesis 1 using hierarchical linear models (HLM) (Bryk & Raudenbush, 1992). Again, the composite measure will be constructed using the methodology described in 2b.

Planned Post-hoc Analyses. Planned post-hoc analyses for the secondary hypotheses are identical to those explained above under the primary hypotheses. These analyses will attempt to explain the variability in the treatment effect.

Hypothesis 2e. BSFT will be significantly more effective than TAU in improving family functioning.

Outcome Variable. The four components of the ‘Parenting Practices Inventory’ will be used to create a composite for use in this analysis. The four component scales from the Parenting Practices Inventory are ‘Positive Parenting’, ‘Discipline Effectiveness,’ ‘Avoidance of Discipline’ and ‘Monitoring’ scales from the Pittsburgh Youth Survey (see Gorman-Smith et al., 1996).

Analysis. Hypothesis 4 will be analyzed as in Hypothesis 1 using hierarchical linear models (HLM) (Bryk & Raudenbush, 1992). Again, the composite measure will be constructed using the methods described in 2b, above.

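### Hypothesis 2c is about sexual risk, but its outcome is scored from survey items that also cover drug-related HIV risk, so a 2c result cannot be read as an effect on sexual behavior

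*Protocol*

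**What the plan says.** The objective in section 2.2 is "Hypothesis 2c: Decreasing adolescent sexually risky behaviors". Section 10.3 repeats it as the claim to be tested: "Hypothesis 2c: BSFT will be significantly more effective than TAU in decreasing sexually risky behaviors".

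The only instrument assigned to 2c is the nine-item Risk Behavior Survey. Section 7.7.5 describes its content: "HIV risk behaviors in the areas of drug use and sex in the previous 30 days are measured".

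Section 10.3 then defines the outcome in two ways. Under the outcome variable, "the total score of the ‘HIV/Sex Risk Behaviors’ measure will be used as the outcome". Under the analysis, "The composite measure will be constructed using the methodology described in hypothesis 2b applied to the items of the Risk Behavior Survey". The method borrowed from 2b starts with a factor analysis: "A confirmatory factor analysis will be conducted to determine that these scales measure a single construct". It then uses equal weights if reliability is sufficient and estimated factor scores if not. Section 10.1.1 adds that, for a scale with alpha below .70, "items with low item-total correlations will be trimmed from the scale and the scale re-assessed for reliability". It also allows the measurement model to be modified when fit is inadequate.

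No section restricts the 2c score to sexual items, defines a sexual-risk subscale, or plans to report the two areas separately.

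**The concern.** The hypothesis names one construct and the score mixes two. Drug use is what the trial mainly sets out to change (Hypothesis 1), so drug-related items are ones that BSFT could plausibly move. If it moves them and leaves sexual behavior unchanged, the 2c test can still come out significant and be reported as a second, separate benefit. In the other direction, drug items that do not respond add noise and weaken a true effect on sexual behavior. Either way, the result does not answer the question that 2c asks.

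This is not a detail left to the SAP. The protocol fixes the outcome as the full score, and an SAP that follows it inherits the mismatch. Elsewhere the protocol does pick out the part of an instrument that fits the construct: Total Delinquency among the five National Youth Survey subscales and the externalizing domain of the Youth Self Report (7.7.4), and the cohesion and conflict subscales of the Family Environment Scale (7.7.7).

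**Working it through.** **Do the stated rules remove the drug items?**

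- The factor analysis asks whether one construct fits. If drug and sexual risk are correlated, one factor may fit well and every item stays.
- If it fits poorly, section 10.1.1 allows changes to the model until CFI and SRMR are acceptable. Nothing says that the retained part must be the sexual items.
- Trimming drops the items least correlated with the total. Those could be drug items or sexual ones.

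None of these rules looks at content.

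**How large could the carry-over be?** The protocol gives no power figure for 2c, so this is an illustration.

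*Inputs from the protocol:* 9 items (7.7.5); 8 sites and an effective 57 per site (10.4); effect size .45 and site variances .10 and .15 (10.4.1); 28% attrition (10.4.1).

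*Assumptions:* 2 or 3 of the 9 items concern drug use; all inter-item correlations are .2; the drug items shift by .45 SD (the trial's planning effect, borrowed); the sexual items do not shift; items are equally weighted; the small site variance is .05, a value that the text does not print.

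*Step 1: composite shift.* The SD of the mean of nine standardised items is √((1 + 8 × .2)/9) = .537.

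- 2 drug items: (2/9 × .45)/.537 = .100/.537 = .186 SD
- 3 drug items: (3/9 × .45)/.537 = .150/.537 = .279 SD

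*Step 2: reproduce the protocol's power.* Section 10.3 analyses 2c as Hypothesis 1, with site as a random effect, so the planning model of 10.4 applies. The noncentrality is λ = J·d²/(σ²δ + 4/n), tested on F with 1 and J − 1 = 7 degrees of freedom at two-sided .05. With J = 8, n = 57 and 4/57 = .0702, d = .45 gives:

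| Site variance | λ | Power | Section 10.4.1 |
|---|---|---|---|
| .05 (assumed) | 8 × .2025/.1202 = 13.48 | 88% | 87% |
| .10 | 8 × .2025/.1702 = 9.52 | 75% | 75% |
| .15 | 8 × .2025/.2202 = 7.36 | 64% | 64% |

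The agreement shows that this is the protocol's model and that .05 is a reasonable reading of small site variability.

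*Step 3: put the composite shifts into the same model.* This gives the chance of a significant 2c result when sexual behavior has not changed:

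| Site variance | 2 drug items (d = .186) | 3 drug items (d = .279) |
|---|---|---|
| .05 | 26% | 50% |
| .10 | 20% | 38% |
| .15 | 16% | 31% |

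With 28% attrition (60 × .72 ≈ 43 per site) the ranges fall to 15–23% and 28–44%. The reference value is 5%, the rate if no item differed between arms.

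**Dilution.** Suppose instead that only the sexual items respond, all by the same amount. The full score's standardised effect, relative to a score of the sexual items alone, is then:

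- 7 sexual items: (7/9)/.537 × √((1 + 6 × .2)/7) = 1.447 × .561 = .81
- 6 sexual items: (6/9)/.537 × √((1 + 5 × .2)/6) = 1.240 × .577 = .72

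Under the same assumptions, about a fifth to a quarter of the effect size is lost.

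**The case against.** The strongest reply is that the consequences are speculative. The item list is in Appendix B and is not shown. The number of drug items, their correlations and their response are all assumed, and the .45 is the planning effect for the trial's main comparison, not for any survey item. That stands: the figures show what could happen and are not estimates.

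Two stronger readings are tempting, and the documents support neither.

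- **That a false 2c result is likely.** A plain two-arm comparison with 240 per arm gives Φ(.186 × √120 − 1.96) = 53% for 2 drug items and Φ(.279 × √120 − 1.96) = 86% for 3. That calculation ignores the random site-by-treatment effect that the protocol builds into this test. The protocol's own model gives roughly a third to a half of the first figure and up to about three fifths of the second.
- **That the 2c outcome overlaps with the primary outcome.** The primary outcome is the percentage of drug use days from the Timeline Follow Back. The survey items are HIV risk behaviors in the area of drug use. An association is plausible, but without the items nobody can show that they move with use days. Nor does the document say that the drug items are rare.

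It is also fair to say that the fit and trimming rules might break up a nine-item equal-weight sum if the two areas separate cleanly. They could help, but by accident rather than design.

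Finally, section 7.7.5 is headed HIV/Sex Risk Behaviors and cites reliability and validity for the survey as an instrument. Keeping the whole score and changing the hypothesis would therefore also be consistent.

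**Conclusion.** The mismatch holds on the protocol's own text. Hypothesis 2c concerns sexual risk only, its outcome is built from items covering drug use and sex, and no rule selects by content. A significant or a null 2c result, as defined, cannot be read as a statement about sexual behavior.

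The size is open. Under the stated assumptions, a drug-item effect alone would give a significant 2c result in about 16–26% of trials (2 drug items) or 31–50% (3 drug items). This rests on the assumed item split, correlation and item effect, on equal weights, and on site variances of .05 to .15 with .05 assumed. The direction of the problem does not depend on those values as long as the score keeps at least one drug item.

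2c is one of five secondary hypotheses. The primary test and the sample size are not touched. The change is worth making because the protocol states the rule, and following it can lead to a wrong conclusion on 2c.

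**What to change.** Before any unblinded outcome analysis:

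1. Define the 2c outcome as the score of the sexual-behavior items of the Risk Behavior Survey, listing the items, and report the drug-risk items separately as a descriptive outcome. Alternatively, keep the full score, reword 2c wherever it appears (sections 2.2, 7.7.5, 10.1 and 10.3) as HIV risk from drug use and sex, and draw no conclusion about sexual risk alone.
2. State whether the outcome is a total score or a factor score; section 10.3 currently allows both.
3. State that trimming or model modification may not change which area the score represents.

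The cost is wording and scoring code. The first option also gives a shorter scale with somewhat lower reliability. No new data are needed. Timing matters, because choosing items after seeing results by arm would look data-driven.

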10.4 Sample Size and Statistical Power

Prior research on BSFT has shown simple (standardized difference) effect sizes in the range of .56 to .68 for drug use, problem behaviors and family functioning (See Appendix A for review of research findings). For engagement into treatment the difference in percentage engagement has varied from 21% to 51% depending on the study. Because power for uncovering significantly differing percentages depends on the base percentage, the effect size is frequently measured as the difference in arcsine square root transformations of the probabilities, which is invariant to the base. Cohen, 1988, calls this effect size index, h . The range of observed h values for BSFT is .23 to .59.

Power analysis for our planned hypotheses are based on the work of Raudenbush and Liu (2000), which describes a model for use with a simple effect in a multi-site clinical trial where the treatment site is treated as a random effect and there is variability in the effect-size across treatment sites. This model assumes equal numbers of participants at each site. Because we prefer not to exclude sites with smaller potential caseloads, it is likely that we will have varying numbers per site. In addition, if smaller samples are balanced with equal numbers of proportionately larger samples, it will be possible to examine these larger sites separately, in a post-hoc analysis. Because variable site size is the limiting case for power, we present the case of variable numbers per site.

[figure not shown]
In both cases we use the same methodology to estimate power; however, in the case of varying numbers per site, we use an adjusted n per site. Following the recommendations of Cohen (1988), when there is variability in sample sizes across conditions, a harmonic mean of the individual sample sizes is computed. The harmonic mean weights the mean more to the smaller sample sizes. Once the harmonic mean is calculated then power estimation continues in the normal fashion. This is clearly an approximation, but should be sufficient for our trial planning.

From examining multiple configurations, we propose that we need 8 sites with approximately 60 participants per site, on average. This results in a total sample size of 480. Because we believe that recruitment rates are relatively consistent across the 8 outpatient sites, we estimate an effective n of 57. Thus, there is a 3 subject per site penalty for allowing the sites to vary in size. With our proposed sample configuration ($n=60$, $J=8$, effective $n=57$), there is nearly 75% power to uncover main effects of treatment with an effect-size of .45 and relatively small site by treatment variability.

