10.4.1 Main Effect of Treatment (Treatment X Time interaction)

Figure 4 (prepared using software provided by [name]) shows the expected power to uncover a significant overall treatment effect when there are 8 sites ($J=8$), the average treatment effect is .45 ($\delta=.45$) and the variability in this effect size is either small, moderate or large ($\sigma_{\delta}^2=.10$, and .15; as coined by Raudenbush & Liu, 2000). As can be seen in the graph, at the point of 57 subjects per site, power is 87% with small site variability, 75% with moderate site variability, and 64% with high site variability.

FIGURE 4. POWER

[figure not shown]

As can be seen in the graph, site variability in effect-sizes may have a substantial effect on power. If we compare the power calculations above with a simple repeated measures power analysis, we see that if there is no variability in effect-sizes across sites, that we have over 80% power to uncover a considerably smaller standardized effect size. We have used the program described in Hedeker, Gibbons, & Waternaux (1999) to calculate power in the case with no variability of effect-size across sites. In this case, there is over 90% power to uncover a Condition X Time interaction with an effect-size of .25 at the last time of assessment. This estimate assumes 28% attrition over the 12-month post-randomization period, a linear growth curve and minimal residual correlation across time ($\rho = .1$). Power actually increases as the correlation of measures across time increases. It is not uncommon for measures such as those used to test the hypotheses in the trial to show correlations across time in the range of .2 to .4, so power may be better than described here. Clearly, if site variability is smaller than the estimates in the graph above, there is substantially more power. On the other hand, if site variability is higher than the estimates in the graph above, there is substantially less power.

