We would further recommend, due to the lack of a compelling reason to expect overwhelming efficacy in this trial, that should an a-priori interim analysis be desired that an O’Brien-Fleming stopping boundary be used (Jennison & Turnbull, 2000). This type of boundary has the least penalty in the final test and involves the lowest inflation factor to sample size necessary to maintain power (Jennison & Turnbull, 2000; Scharfstein, Tsiatis & Robins, 1997). The critical value for the interim analysis would be 2.7959 (corresponding to a p-value of .0052), whereas the critical value for the final test would be 1.977 (corresponding to a p-value of .048). To maintain power levels the sample would need to be increased from 840 to 848.

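### Section 10.4 attaches the moderate-variability power (75%) to small site variability, leaves unsaid that its multi-site figures are before attrition, and Section 13 inflates a sample of 840 instead of 480

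*Protocol*

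**What the plan says.** Section 10.4 of the Protocol sets the size of the trial: "we need 8 sites with approximately 60 participants per site, on average". It adds "This results in a total sample size of 480" and, because sites will differ in size, "we estimate an effective n of 57". The reason for the reduction is given as "there is a 3 subject per site penalty for allowing the sites to vary in size". The summary of power is then "there is nearly 75% power to uncover main effects of treatment with an effect-size of .45 and relatively small site by treatment variability".

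Section 10.4.1 describes the same configuration (8 sites, 57 per site, effect .45) and reports that "power is 87% with small site variability, 75% with moderate site variability, and 64% with high site variability". Further on it turns to a different calculation, a repeated-measures comparison with no site variability and an effect of .25. For that one only, it says "This estimate assumes 28% attrition over the 12-month post-randomization period".

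Section 13 plans no interim efficacy analysis. It recommends an O'Brien-Fleming boundary in case the DSMB wants one, with critical values 2.7959 and 1.977, and says that "the sample would need to be increased from 840 to 848" to keep power.

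**The concern.** Three statements do not fit together.

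- **Label.** The sentence that justifies the design gives small site variability a power that the next subsection gives to moderate variability. A reader of Section 10.4 alone cannot tell whether the favourable case has 75% or 87% power, or that power is below 80% once variability is moderate. Section 13 says that variability is expected to be higher than in efficacy trials, because usual treatment differs by site, so the moderate and high cases are the ones to look at.
- **Attrition.** The multi-site powers use 57 per site with no loss to follow-up, while the neighbouring calculation assumes 28%. The text does not say that the two rest on different assumptions.
- **Interim inflation.** A DSMB that took up the contingent recommendation would read a sample size that is not this trial's.

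**Working it through.** **Inputs.** Sites J = 8, effective n = 57 per site and effect δ = .45 come from Sections 10.4 and 10.4.1. The model is the multi-site random-effects model named in Section 10.4. Section 10.4.1 prints only two variances, .10 and .15, for three labels. I take them as moderate and large and assume .05 for small. Allocation is 1:1 (Section 10.4.2 has 30 per group at a site of 60). Section 10.4 does not state sidedness; I assume two-sided 5%.

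**Formula.** Power is the upper tail of a noncentral F(1, J − 1) beyond its 5% critical value, F(1, 7) = 5.59, with noncentrality λ = Jδ²/(σ² + 4/n). Here Jδ² = 8 × .45² = 1.62.

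**Reproducing the plan's figures, n = 57 (4/n = .0702):**

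| Variance | λ | Power | Section 10.4.1 |
|---|---|---|---|
| .05 | 1.62/.1202 = 13.48 | 88.1% | 87% (small) |
| .10 | 1.62/.1702 = 9.52 | 75.4% | 75% (moderate) |
| .15 | 1.62/.2202 = 7.36 | 64.5% | 64% (high) |

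All three agree within about one point. A one-sided test (95/87/79%) and a normal approximation (96/87/77%) do not fit. Solving for the variance that gives exactly 75% yields about .102, the moderate level. The number in the Section 10.4 sentence is therefore sound and its label is not. For small variability it is about 12 to 13 points too low.

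**Attrition.** The match at n = 57 confirms that no loss is built in. As a worst case, let 28% of participants contribute no information: n = 57 × .72 = 41.04 and 4/n = .0975.

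| Variance | λ | Power | Fall from n = 57 |
|---|---|---|---|
| .05 | 1.62/.1475 = 10.99 | 81.0% | 7 points |
| .10 | 1.62/.1975 = 8.20 | 69.2% | 6 points |
| .15 | 1.62/.2475 = 6.55 | 59.6% | 5 points |

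If half of that information were lost instead (n = 57 × .86 = 49.02), power would be 85%, 73% and 62%.

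**Interim inflation.** A two-look O'Brien-Fleming design at overall two-sided 5% gives critical values 2.797 and 1.977 (p = .0052 and .048), as Section 13 states. The protocol's ratio is 848/840 = 1.0095, and 480 × 1.0095 = 484.6, so about 485. Solving for the inflation directly gives a factor of 1.007 to 1.008 for power between 75% and 90%, so about 484.

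**The case against.** The label slip is corrected by the very next subsection, it understates power and so is conservative, and no sample-size number changes. The 840 stands in advice that applies only if the DSMB asks for an interim plan, and the 4 or 5 extra participants fit within the 480 or more that Section 4.1 allows. All of that is true. It limits the harm, but both statements remain wrong as written.

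The objection has more force on attrition. The 28% is not ignored throughout, since Section 10.4.1 uses it once. Section 10.1.1 keeps incomplete cases through maximum likelihood and continues to assess those who leave treatment, so partial follow-up counts. The multi-site method, which Section 10.4 calls an approximation, also gives no credit for repeated measures or for the baseline covariate in Section 10.2.1. A reader might infer that power is really 69% in the moderate case. The documents do not support that: 69% is a lower bound under this approximation.

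A reader might also infer that the claim in Section 10.4.1 of over 90% power for an effect of .25 is wrong. With 240 per arm, exchangeable correlation .1, linear 28% dropout and a two-sided test, I get 84% (13 times) or 81% (12 times) with a free group intercept. With the arms constrained equal at baseline I get about 98%. Section 10.4.1 does not say which model was used, so no error is shown.

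**Conclusion.** The point holds in a limited form. Section 10.4 contradicts Section 10.4.1 on its face, and recalculation supports Section 10.4.1. The contradiction does not depend on any assumption; the numerical check assumes .05 for small variance and a two-sided 5% test, and Figure 4 itself was not available to check.

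The multi-site powers are before attrition and should say so. The most that 28% attrition can cost under the same approximation is about 7, 6 and 5 points at small, moderate and large variability.

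The 840 in Section 13 has no counterpart in a plan for 480. It looks like a remnant of another design, since the same section still refers to a residential-versus-outpatient interaction that an eight-site outpatient trial does not have.

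It would go too far to say that the power calculation as a whole is wrong. The 87/75/64% figures and the interim critical values all reproduce for their inputs, and the planned 480 is unaffected.

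**What to change.** In Section 10.4, replace the summary sentence with one saying that power is about 87%, 75% and 64% for small, moderate and large site variability, before attrition; and that in the worst case, with all information lost from 28% of participants, it is not lower than about 81%, 69% and 60% under the same approximation.

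In Section 13, change the inflation to read from 480 to about 485.

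Leave the over-90% statement for the effect of .25 as it stands.

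The cost is wording only. The stated power reads slightly less favourably, and planned enrolment does not change.
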